10.1 Demographic Variables

The demographic variables collected in this study include age, sex, childbearing potential, race, ethnicity, and iris color (right eye [OD] and left eye [OS]). Subjects can select more than one race, and they will be categorized as Multiple Race on summaries. Demographic variables will be summarized for the FAS, COVID-19 Analysis Set, PP set, and Safety set separately. Demographic variables will also be summarized by site for the FAS.

Age (years) will be summarized by treatment arm and overall using continuous descriptive statistics as well as dichotomized into age categories of <65 years and ≥65 years. Age will be reported in years and calculated using the age at last birthday.

The number and percentage of subjects will be presented by treatment arm and overall for sex, childbearing potential, race, ethnicity, and iris color (OD and OS).

A subject listing that includes age, sex, race, ethnicity, and iris color will be provided. Childbearing potential will be listed with urine pregnancy results (see [Section 15.2](#)).

Tables and listings for demographics and pre-treatment variables will be generated after the completion of Milestone 1, as described in [Section 2.7](#).

11. Medical History and Concomitant Medications

Tables and listings for medical history will be generated after the completion of Milestone 1, as described in [Section 2.7](#).

As described in [Section 2.7](#), tables, and listings for concomitant medications and procedures with a start date during the on-treatment interval will be generated after Milestone 1. These tables and listings will use all available data and thus, concomitant medications and procedures with start dates during the on-treatment interval and end dates after Day 43/57 will be shown in Milestone 1 tables and listings. After the completion of Milestone 2, the concomitant medication and procedures listings, and the on-treatment interval tables will be re-run to include the Day 90/post-treatment interval data. Additionally, separate tables

for concomitant medications and procedures with start dates during the post-treatment interval will be generated for Milestone 2.

11.1 Medical History

Medical history will be coded using the Medical Dictionary for Regulatory Activities (MedDRA) Version 23.0.

Ocular medical history will be summarized using discrete summary statistics and presented by treatment arm at the subject level by System Organ Class (SOC) and Preferred Term (PT) using the Safety set. Non-ocular medical history will be similarly summarized at the subject level. Medical history will be summarized by PT and SOC at the subject level. A subject will only be counted once even if they have multiple histories for a given classification. All SOCs and PTs within an SOC will be sorted in decreasing frequency among all subjects.

Listings of medical history will be generated separately for ocular and non-ocular data.

11.2 Concomitant Medications

Concomitant medications will be coded using World Health Organization Drug Dictionary (WHODrug) Global (B3, March 2020) and summarized by therapeutic drug class (Anatomical Therapeutic Chemical [ATC] 4 classification) and preferred name. If the ATC 4 classification is not provided, the next lowest classification that is provided in the coding dictionary will be used. The preferred name will be defined as the active ingredient; if the active ingredient is not provided or includes more than two ingredients (e.g., multivitamins) then the drug name will be summarized as the preferred name.

Concomitant medications are defined as those medications reported as having been taken (1) prior to initiation of study drug administration and continuing for any period of time following the first administration of study drug or (2) at any time following the first administration of study drug.

Concomitant medications will be summarized using the Safety set. Medications will be tabulated for each treatment arm using frequencies and percentages. Subjects may have more than one medication per ATC text. At each level of subject summarization, a subject will be counted once if he/she reports one or more medications. Percentages will be based on the number of subjects in each treatment arm. The ATC classes and preferred names within an ATC class will be sorted in decreasing frequency among all subjects. Listings of concomitant medications will be generated separately for ocular and non-ocular data (as specified by the investigator), including indication, route of administration, start date, and end date or ongoing.

11.3 Concomitant Procedures

Concomitant procedures will be coded using the Medical Dictionary for Regulatory Activities (MedDRA) Version 23.0 and summarized by SOC and PT.

Concomitant procedures will be summarized using the Safety set. Procedures will be tabulated for each treatment arm using frequencies and percentages. Subjects may have more than one procedure per PT. At each level of subject summarization, a subject will be counted once if he/she reports one or more procedures. Percentages will be based on the number of subjects in each treatment arm. All SOCs and

PTs within an SOC will be sorted in decreasing frequency among all subjects. Listings of concomitant procedures will be generated separately for ocular and non-ocular data (as specified by the investigator).

12. Dosing Compliance

12.1 Dosing Compliance

Dosing compliance (% compliance) will be assessed by calculating the number of actual doses received and comparing that to the number of expected doses as follows:

$$\text{Compliance (\%)} = \frac{\text{Number of Actual Doses Received} \times 100\%}{\text{Number of Expected Doses}}$$

The number of actual doses received will be recorded in the CRF (first dose in Study Drug Instillation CRF and remaining doses in Study Drug Diary CRF). Two doses are expected each day except only one dose should be completed on the last day of the study. The number of expected doses that will be used for calculating compliance will be calculated as:

$$2 \times (\text{Date of Last Dose} - \text{Date of First Dose}) + 1$$

for all subjects, regardless of study completion status. Date of last dose will be taken from the last date the study drug was taken from the subject diary or the study drug instillation page of the eCRF, whichever is later. In the case where drug was temporarily withdrawn, the number of days without study drug will be accounted for by subtracting 2 doses per day without study drug.

A categorical dosing compliance variable will also be derived as non-compliant (<80%), compliant ($\geq 80\%$ and $\leq 125\%$), and over compliant ($>125\%$).

Dosing compliance (%) will be summarized with continuous descriptive statistics for each treatment arm, as well as by site, sex, age group, and race using the Safety set. The compliance category defined above will be summarized with discrete summary statistics.

A subject listing of dosing compliance will also be produced after Milestone 1.

13. Efficacy Analyses

All efficacy analyses, as well as the generation of tables, listings, and figures, will be performed after the completion of Milestone 1, as described in [Section 2.7](#).

Study efficacy assessments performed include the following:

- Assessment of collarette grade
- Eyelash epilation and mite counts
- Assessment of erythema grade

Collarette grade (score) is determined based on number of lashes with collarettes per eyelid (Table 3). The proportion of subjects cured in the upper eyelid of the analysis eye based on collarette grade will be summarized by visit and treatment arm. The percentage of subjects at each grade will be summarized by visit and treatment arm, as well as by site, sex, age group, and race. The mean collarette score and change from Baseline in collarette score will be summarized by visit and treatment arm. The proportion of subjects cured (Collarette Grade 0) in the upper eyelid of the analysis eye, and the change from baseline in the mean collarette score in the upper eyelid of the analysis eye by visit and treatment arm, will be displayed graphically by bar charts.

Table 3. Collarette Grading

Grade	Clinical Interpretation
0	0 to 2 lashes have collarettes per eyelid
1	3 to 10 lashes have collarettes per eyelid
2	More than 10 but less than $\frac{1}{3}$ of lashes have collarettes per eyelid
3	$\frac{1}{3}$ or more but less than $\frac{2}{3}$ of lashes have collarettes per eyelid
4	$\frac{2}{3}$ or more of lashes have collarettes per eyelid
0.5-unit increments ARE NOT allowed	

Mite density in the analysis eye and change from baseline will be summarized by visit and treatment arm, as well as by site, sex, age group, and race. Mite density is the total number of mites counted divided by the total number of lashes epilated. The proportion of subjects with *Demodex* eradication will be summarized by visit and treatment arm, as well as by site, sex, age group, and race. The mean mite density and change from Baseline in collarette score will be summarized by visit and treatment arm. The proportion of subjects with *Demodex* eradication (Mite Density 0) in the analysis eye, and the change from baseline in mean mite density in the analysis eye by visit and treatment arm, will be displayed graphically by bar charts.

Erythema of the eyelid margin is graded on a scale from 0 (normal) to 3 (severe erythema) (Table 4). The percentage of subjects at each grade level in the upper eyelid of the analysis eye will be summarized by visit and by treatment arm, as well as by site, sex, age group, and race. The mean erythema score and change from Baseline in collarette score will be summarized by visit and treatment arm. The proportion of subjects with erythema cure (erythema grade 0) in the upper eyelid of the analysis eye, and the change from baseline in mean erythema score in the upper eyelid of the analysis eye by visit and treatment arm, will be displayed graphically with bar charts.

Table 4. Lid Margin Erythema Grading

Grade	Severity	Clinical Interpretation
0	Normal	Normal age-related lid coloration
1	Mild	Pink capillary involvement along the lid edge, no patches of confluent capillary redness throughout the lid edge
2	Moderate	Deep pink or red confluent capillary redness present locally along the lid edge
3	Severe	Deep red, diffuse confluent capillary redness present along the lid edge
0.5-unit increments ARE NOT allowed		

The proportion of subjects' composite cure based on collarette of 0 and erythema score of 0 will be summarized by visit and by treatment arm, as well as by site, sex, age group, and race. The proportion of subjects with composite cure in the upper eyelid of the analysis eye by visit and treatment arm will be displayed graphically with bar charts.

13.1 Primary Analysis

The primary efficacy endpoint is cure defined as collarette score of 0 for the upper eyelid of the analysis eye at Day 43. Descriptive statistics will be presented by treatment arm. Testing of the percentage of subjects cured at Day 43 based on the collarette grade will be completed using a difference of proportions test.

The primary efficacy endpoint analysis will be conducted on the FAS, with intercurrent events handled as described in [Section 2.6](#). Discontinuation of study medication and non-optimal compliance will be ignored. Missing data due to withdrawal due to lack of efficacy or AEs will be imputed as failure. Missing data without withdrawal or withdrawal due to reasons other than lack of efficacy or AEs will be imputed employing MI using randomized treatment-based MCMC methodology. The MCMC method simulates missing data under a missing at random assumption while accounting for the uncertainty in the imputed values. Missing values will be imputed with an arbitrary missing pattern. The procedure will use the posterior mode from the EM algorithm as the starting values for the MCMC method. The following SAS® code will be used to generate the multiple imputation datasets:

```
PROC MI DATA=INDATA SEED=19107 NIMPUTE=20 OUT=OUT1 MINIMUM=0 MAXIMUM=4 ROUND=1;
  BY TRT;
  MCMC INITIAL=EM;
  VAR BASE DAY08 DAY15 DAY22 DAY43;
RUN;
```

where

- INDATA is the name of the input dataset
- OUT1 is the name of the output dataset
- TRT is the name of the treatment group variable
- BASE is the baseline assessment
- DAY08 is the assessment at Day 8
- DAY15 is the assessment at Day 15
- DAY22 is the assessment at Day 22
- DAY43 is the assessment at Day 43

The MI datasets will be used to calculate cure based on a collarette score of 0 at Day 43. The following SAS® code will then be used to calculate the difference of proportions for each imputed dataset and combine the analyses across imputations:

```
PROC SORT DATA=OUT1; BY _IMPUTATION_; RUN;
```

where

- OUT1 is the name of the input dataset
- _IMPUTATION_ is the imputation number

and

```
PROC FREQ DATA=OUT1;
  BY _IMPUTATION_;
  TABLES TRT*CURE / RISKDIFF CL;
  ODS OUTPUT RISKDIFFCOL2=PROP;
RUN;
```

where

- OUT1 is the name of the input dataset
- _IMPUTATION_ is the imputation number
- TRT is the name of the treatment group variable
- CURE is the indicator for cure based on a collarette score of 0 at Day 43
- PROP is the name of the output dataset

and

```
PROC MIANALYZE DATA=PROP;
  WHERE ROW='Difference';
  MODELEFFECTS RISK;
  STDERR ASE;
  ODS OUTPUT PARAMETERESTIMATES=PEST;
RUN;
```

where

- PROP is the name of the input dataset

Statistical comparison between treatment arms will be one-sided using an α of 0.025.

In addition to the primary analysis, sensitivity analyses as described in [Section 13.1.1](#) will be conducted to assess the endpoint under different assumptions of missingness.

Furthermore, the primary endpoint of the proportion of subjects cured based on a collarette score of 0 will be analyzed at all visits in the upper eyelid of the analysis eye, the upper eyelid of the fellow eye, the lower eyelid of the analysis eye, and the lower eyelid of the fellow eye using observed data only. Separate stratified analyses will be conducted for the upper eyelid of the analysis eye by site, sex, age group, and race on the FAS using observed data only, unless p-values are not calculable due to sparsity of sample size limitations. In addition, if the COVID-19 Analysis Set consists of $\leq 95\%$ of study subjects, the analysis will be conducted for the upper eyelid of the analysis eye at Day 43 on the COVID-19 Analysis Set with observed data only. These analyses will be conducted using similar SAS® code as described in [Section 13.1.1.3](#).

13.1.1 SENSITIVITY ANALYSES

The following sensitivity analyses will be conducted on the primary efficacy endpoint.

13.1.1.1 SENSITIVITY ANALYSIS I

The primary efficacy analysis will be performed on the FAS set using the difference of proportions test. The hypothetical strategy introduced in [Section 2.6](#) will be used for the intercurrent event, where missing data will be imputed assuming missing not at random (imputing from the vehicle treatment arm). Discontinuation of study medication and non-optimal compliance will be ignored. The following SAS® code will be used to generate the MI datasets:

```
PROC MI DATA=INDATA SEED=43623 NIMPUTE=20 OUT=MDATA MINIMUM=0 MAXIMUM=4 ROUND=1;
  BY TRT;
  MCMC IMPUTE=MONOTONE;
  VAR BASE DAY08 DAY15 DAY22 DAY43;
RUN;
PROC MI DATA=MDATA SEED=346238 NIMPUTE=1 OUT=OUT1 MINIMUM = . 0 0 0 0 0 MAXIMUM
= . 4 4 4 4 4 ROUND = . 1 1 1 1 1;
  BY _IMPUTATION_;
  CLASS TRT;
  MONOTONE REG(DAY08 = BASE/DETAILS);
  MONOTONE REG(DAY15 = BASE DAY08/DETAILS);
  MONOTONE REG(DAY22 = BASE DAY08 DAY15/DETAILS);
  MONOTONE REG(DAY43 = BASE DAY08 DAY15 DAY22/DETAILS);
  MNAR MODEL(BASE DAY08 DAY15 DAY22 DAY43 / MODELOBS=(TRT='Vehicle'));
  VAR BASE DAY08 DAY15 DAY22 DAY43;
RUN;
```

13.1.1.2 SENSITIVITY ANALYSIS II

The primary efficacy analysis will be performed on the FAS set using the difference of proportions test. The hypothetical strategy introduced in [Section 2.6](#) will be used for the intercurrent event, where missing data will be imputed assuming missing at random (imputing from the same treatment arm as the subject with missing data) using similar code as provided in [Section 13.1](#) for the primary efficacy analysis. Discontinuation of study medication and non-optimal compliance will be ignored.

13.1.1.3 SENSITIVITY ANALYSIS III

The primary efficacy analysis will be performed on the PP set with observed data only using the difference of proportions test. In addition, a Fisher's exact test will be performed. The following SAS® code will be used to generate the analyses:

```
ODS OUTPUT CHISQ = OUT_CHISQ FISHERSEXACT = OUT_F;
PROC FREQ data = INDATA;
  TABLES TRT * OTCM / FISHER EXPECTED OUTEXPECT OUT = OUT_EXP;
RUN;
```

Where

- INDATA is the name of the input dataset
- TRT is the name of the treatment group variable
- OTCM is the indicator for cure based on a collarette score of 0 at Day 43
- OUT_CHISQ is the name of the output dataset that will contain the p-value for the difference of proportions test when all expected cell counts are at least 5
- OUT_F is the name of the output dataset that will contain the p-value for the Fisher's exact test and the difference of proportions test when any expected cell count is < 5
- OUT_EXP is the name of the output dataset that will contain the expected cell counts

13.1.1.4 SENSITIVITY ANALYSIS IV

The primary efficacy analysis will be performed on the FAS set with observed data only using the difference of proportions test. In addition, a Fisher's exact test will be performed. Analyses will be conducted using similar SAS® code as described in [Section 13.1.1.3](#).

13.1.1.5 SENSITIVITY ANALYSIS V

The primary efficacy analysis will be performed on the FAS set using the difference of proportions test. The hypothetical strategy introduced in [Section 2.6](#) will be used for the intercurrent event where missing data will be imputed as failure. Discontinuation of study medication and non-optimal compliance will be ignored. In addition, a Fisher's exact test will be performed.

13.2 Secondary Analyses

The secondary efficacy endpoints are the proportion of subjects with *Demodex* eradication (mite density of 0 mites/lash) at Day 43; the proportion of subjects cured based on a composite collarette and erythema score of 0 at Day 43; and the proportion of subjects cured based on an erythema score of 0 at Day 43. All secondary endpoint analyses will be conducted on the FAS.

As specified in [Section 8.2](#), missing data without withdrawal or withdrawal due to reasons other than lack of efficacy or AEs will be imputed employing MI using randomized treatment-based MCMC methodology.

The following SAS® code will be used to generate the MI datasets:

```
PROC MI DATA=INDATA SEED=10719 NIMPUTE=20 OUT=OUT1 MINIMUM=0 MAXIMUM=4 ROUND=1;
  BY TRT;
  MCMC INITIAL=EM;
  VAR BASE DAY08 DAY15 DAY22 DAY43;
RUN;
```

The MI datasets will be used to calculate cure based on each respective secondary endpoint. The following SAS® code will then be used to calculate the difference of proportions for each imputed dataset and combine the analyses across imputations:

```
PROC SORT DATA=OUT1; BY _IMPUTATION_; RUN;
PROC FREQ DATA=OUT1;
  BY _IMPUTATION_ ;
  TABLES TRT*CURE / RISKDIFF CL;
  ODS OUTPUT RISKDIFFCOL2=PROP;
RUN;
PROC MIANALYZE DATA=PROP;
  WHERE ROW='Difference';
  MODELEFFECTS RISK;
  STDERR ASE;
  ODS OUTPUT PARAMETERESTIMATES=PEST;
RUN;
```

Comparisons will be one-sided using an α of 0.025.

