**Day 8 ± 3 days      Follow-up assessments of study endpoints and safety**

- Concomitant medication review
- [REDACTED]
- CDVA
- Slit lamp biomicroscopy
- Collarette grading; erythema assessment
- Corneal staining
- [REDACTED]
- Collection of study drug and return to participant
- Adverse event review and evaluation

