13.2.1 SECONDARY EFFICACY ENDPOINTS

The first secondary efficacy endpoint is the proportion of subjects cured at Day 43, as defined by *Demodex* eradication (mite density of 0 mites/lash) in the analysis eye. Descriptive statistics will be presented by treatment arm.

Analysis will be conducted on the FAS, with intercurrent events handled as described in [Section 2.6](#). Discontinuation of study medication and non-optimal compliance will be ignored. Missing data due to withdrawal due to lack of efficacy or AEs will be imputed as failure. Missing data without withdrawal or withdrawal due to reasons other than lack of efficacy or AEs will be imputed employing MI using randomized treatment-based MCMC methodology as described in [Section 13.1](#). Testing of the percentage of subjects cured at Day 43 based on the *Demodex* eradication will be completed using a difference of proportions test.

In addition, a sensitivity analysis will be conducted in which all missing data will be imputed as failure. The difference of proportions test and Fisher's exact test will be used in this sensitivity analysis. Furthermore, the proportion of subjects cured based on *Demodex* eradication will be analyzed at all visits in both the analysis and fellow eye using observed data only. Stratified analyses will be conducted for the upper eyelid of the analysis eye by site, sex, age group, and race on the FAS using observed data only, unless p-values are not calculable due to sparsity or sample size limitations. In addition, if the COVID-19 Analysis Set consists of ≤95% of study subjects, the analysis will be conducted for the upper eyelid of the analysis eye at Day 43 on the COVID-19 Analysis Set with observed data only. These analyses will be conducted using similar SAS® code as described in [Section 13.1.1.3](#).

The second secondary efficacy endpoint is the proportion of subjects cured at Day 43, as defined by a composite score of 0 based on collarette and erythema scores in the analysis eye. Descriptive statistics will be presented by treatment arm.

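### SAP 13.2 reuses the collarette imputation code for Demodex eradication, so imputed eradication follows residual mite density instead of the eradication rate

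*SAP*

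**What the plan says.** SAP 13.2 names Demodex eradication first among the secondary endpoints and then prints the code to be used: "PROC MI DATA=INDATA SEED=10719 NIMPUTE=20 OUT=OUT1 MINIMUM=0 MAXIMUM=4 ROUND=1", run by treatment arm with MCMC and the variable list "VAR BASE DAY08 DAY15 DAY22 DAY43". Only the seed differs from the collarette block in SAP 13.1. The SAP continues: "The MI datasets will be used to calculate cure based on each respective secondary endpoint".

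SAP 13.2.1 gives eradication no model of its own. Missing values "will be imputed employing MI using randomized treatment-based MCMC methodology as described in" section 13.1, which contains only the collarette code. The input is described no further than "DAY43 is the assessment at Day 43".

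SAP section 13 defines the quantity to be imputed: "Mite density is the total number of mites counted divided by the total number of lashes epilated". Eradication is a density of 0. The protocol's Day 8 visit lists "Collarette grading; erythema assessment" but no Demodex count, and the schedule in SAP 3.2 also leaves the count blank at Day 8. Counts are scheduled at Days 15, 22 and 43.

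SAP 13.2.1 also plans two supportive analyses of eradication that do not use this code. One sets all missing data to failure. In the other, eradication "will be analyzed at all visits in both the analysis and fellow eye using observed data only".

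**The concern.** The options suit a collarette grade: an integer from 0 to 4, graded at Day 8. Mite density differs on each count. It is a fraction, it has a point mass at 0, no maximum is stated, and it has no scheduled Day 8 value.

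The rounding does the damage. With `ROUND=1`, an imputed density below 0.5 becomes 0 and counts as eradicated, while an observed 0.25 counts as not eradicated. Without rounding, a continuous draw is never exactly 0, so no imputed subject would ever be eradicated. The imputed rate is therefore set by the mean and spread of density, not by how often mites were eradicated.

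This is the main analysis of an endpoint in the Hochberg family (SAP 8.5), and its population-level summary is the difference in proportions (SAP 2.6). That difference, the two rates and the confidence interval are at stake, in a direction not known in advance.

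**Working it through.** **1. The plan's own figure.** SAP section 5 gives 99% power for eradication with 150 per arm, 73.3% vs 21.1%, one-sided 0.025, and more than 99% at the Saturn-1 rates 67.9% vs 17.6%. With pooled variance under the null:

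z = [(p1 - p2)√n - 1.96√(2p̄(1 - p̄))] / √[p1(1 - p1) + p2(1 - p2)]

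This gives z = 8.3 and 7.9, so power is above 99.9% in both cases. The stated figures reproduce, and the test result has ample margin.

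**2. Share imputed as eradicated, closed form.** Let p be the true eradication rate and d the mean density in subjects not eradicated. The documents do not give d. Assume a coefficient of variation of 0.71 (squared, 0.5) among those subjects. The normal model then sees

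- mean m = (1 - p)d
- variance s² = (1 - p)d²(1.5) - m²

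With the limits 0 and 4 checked before rounding, the share imputed as 0 is

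[Φ((0.5 - m)/s) - Φ((0 - m)/s)] / [Φ((4 - m)/s) - Φ((0 - m)/s)].

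With limits checked after rounding, 0 and 4 become -0.5 and 4.5. The documents do not fix the order, so both are shown.

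Example, TP-03 with p = 0.679 and d = 1: m = 0.321, s = 0.615. Before rounding: (0.615 - 0.301)/(1 - 0.301) = 44.9%. After rounding: (0.615 - 0.091)/(1 - 0.091) = 57.6%. The true rate is 67.9%.

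| d (mites/lash) | TP-03 imputed (true 67.9%) | Vehicle imputed (true 17.6%) |
|---|---|---|
| 0.2 | about 100% | 98.6-98.8% |
| 0.5 | 80.7-86.3% | 53.0-59.0% |
| 1.0 | 44.9-57.6% | 22.8-30.6% |
| 1.5 | 29.6-42.5% | 14.1-20.8% |
| 2.0 | 22.0-33.7% | 10.7-16.3% |
| 3.0 | 15.4-24.7% | 8.8-13.4% |

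The true rate is fixed within each column; only d changes.

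**3. Shift in the treatment difference.** With a fraction f of Day 43 values filled by imputation and data missing completely at random:

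shift = f × [(imputed TP-03 rate - 67.9) - (imputed vehicle rate - 17.6)]

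Example, d = 0.5 on TP-03 and 2 on vehicle, limits after rounding, f = 0.30: 0.30 × [(86.3 - 67.9) - (16.3 - 17.6)] = 0.30 × 19.7 = +5.9 points.

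| d TP-03 / vehicle | 5% missing | 15% | 30% |
|---|---|---|---|
| 0.2 / 0.2 | -2.5 | -7.4 | -14.7 |
| 0.5 / 0.5 | -1.2 | -3.5 | -6.9 |
| 1.0 / 1.0 | -1.2 | -3.5 | -7.0 |
| 1.5 / 1.5 | -1.4 | -4.3 | -8.6 |
| 1.0 / 2.0 | -0.4 | -1.3 | -2.7 |
| 0.5 / 2.0 | +1.0 | +3.0 | +5.9 |
| 0.2 / 2.0 | +1.7 | +5.0 | +10.0 |

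**4. Simulation of the procedure (Python, not SAS).** By-arm multivariate normal data augmentation on baseline, Day 15, Day 22 and Day 43 density. Day 8 was left out because it has no data. Assumptions: 209 per arm; Saturn-1 rates at Day 43; Day 15/22 eradication 35%/50% on TP-03 and 10%/14% on vehicle; correlation 0.5 between adjacent visits; 4 or 8 lashes; d from 0.5 to 1.5 on TP-03 and 0.5 to 3.0 on vehicle, never below TP-03; dropout plus about 4% intermittent gaps, completely at random or 1.5 times as likely after a non-zero Day 15 count; 100 trials with 8 imputations per setting (5 for the logistic runs).

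| | 5% missing | 15% | 30% |
|---|---|---|---|
| Shift, printed options (points) | -1.9 to +1.4 | -5.3 to +3.9 | -10.5 to +7.4 |
| Median size of shift | 1.1 | 3.1 | 5.9 |
| Mean coverage of 95% CI | 95% | 90% | 77% |
| Shift, logistic imputation of status | -0.3 to +0.3 | -0.6 to +0.5 | -1.3 to +0.4 |

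Monte Carlo standard errors are at most 0.14, 0.22 and 0.35 points. The cap of 4 alone changes results by at most 0.4 points. The observed-data analysis stayed within 0.9 points throughout. Eradication was significant in every simulated trial.

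**5. Other inputs.** Entering mite counts does not help: rounding would fit, but the limit of 4 would not, and the shift at 30% missing is -13.6 to -8.0. Entering a 0/1 status gives, by the method of step 2 at 30% missing, -1.7 to -2.8 points if any value of 1 or more counts as success, and -2.8 to -4.1 if only exactly 1 does.

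**The case against.** The strongest reply is that the block is a template. One block serves three endpoints, composite cure needs two scores, and erythema stops at grade 3, so a programmer must adapt it anyway. On this view the SAP has a specification gap, not a wrong analysis. The wording does not support that: section 13.2 states that the printed code will be used, whereas elsewhere the SAP says similar code where adaptation is meant. If variable, rounding and limits are left to the programmer, the main analysis is not prespecified.

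A 0/1 input would shrink the error. It is an unnatural reading, because cure is calculated after imputation, and it still shifts the difference.

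The size does rest on assumptions. Residual density, lash count, early eradication rates and missing rate are not in the documents, and the 30% figure in SAP section 5 allows for COVID-19 and site closures. At 5% missing the median shift is 1.1 points and coverage is nominal. The simulated ranges are also not bounds: residual densities near 0.2 go beyond them, as step 3 shows. These limits stand.

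Two planned analyses avoid the defect: observed data, and missing set to failure. They are useful, but they are supportive and do not repair the main estimate. They could expose a discrepancy only after unmasking, when changing the main analysis is hard to defend.

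**Conclusion.** The concern holds. The mismatch between code and endpoint is certain from the text; its size is not. Under the stated assumptions it is about one point on the treatment difference at 5% missing, about 3 at 15% and about 6 at 30% (medians), in either direction. Interval coverage falls to about 90% and 77% at the two higher rates. These figures treat all missing data as multiply imputed. Withdrawals for lack of efficacy or adverse events are set to failure, which lowers the imputed share.

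With an expected difference of about 50 points (67.9 - 17.6 = 50.3), the significance conclusion is not threatened, and the primary endpoint is untouched. The point should be fixed because the main estimate of a multiplicity-controlled endpoint would otherwise score imputed subjects by a different rule from observed ones.

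**What to change.** Before unmasking:

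1. Give eradication its own code. Within arm, impute Day 43 eradication (yes/no) by a logistic model from baseline density and Day 15 and Day 22 eradication status, by fully conditional specification so that intermittent gaps are handled. Drop the Day 8 variable, the cap of 4 and the rounding. Density at Days 15 and 22 may replace status; both were simulated and both lie within the ranges above, but the SAP should name one. State the seed and the number of imputations (20, as now). Withdrawals for lack of efficacy or adverse events stay failures. Mean coverage with this model was 94-95%.
2. Align the MCMC wording for this endpoint in SAP 2.6, 8.2, 13.2 and 13.2.1. Record the departure from protocol 9.4.2 and 9.4.3 in SAP section 17, which now reports no changes.

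As a separate clarification, state that composite cure is derived from the imputed collarette and erythema scores.

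The cost is SAP text and code; no new data are needed. The downside is a departure from the imputation method named in the protocol. Protocol 9.4.1 gives the SAP precedence, so this is permitted if it is recorded.
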